8.2 NON-INVESTIGATIONAL MEDICINAL PRODUCT(S)

The following classes of drugs are identified as non-investigational medicinal products (NIMP) because the medication is either a background therapy or a potential rescue medication for elevated TG:

- Statins (atorvastatin, rosuvastatin, simvastatin)
- Fenofibrate

Please see [Section 8.9](#) for further information.

8.3 BLINDING PROCEDURES

8.3.1 Methods of blinding

Alirocumab and placebo for alirocumab will be provided in identically matched auto injector and packaged identically which includes labeling to protect the blind.

Ezetimibe and placebo for ezetimibe will be provided in identically matched caps and packaged identically which includes labeling to protect the blind.

Each double-blind treatment kit will be labeled with a number, which will be generated by a computer program from Sanofi. The treatment kit numbers will be obtained by the investigator at the time of patient randomization and subsequent patient visits scheduled via a centralized treatment allocation system that will be available 24 hours-a-day, 7 days-a-week.

In accordance with the double-blind design, study patients, investigators and study site personnel will remain blinded to study treatment and will not have access to the randomization (treatment codes) except under circumstances described in [Section 8.3.2](#).

8.3.1.1 *Lipid parameters*

Lipid parameter values from blood samples obtained after the randomization visit, run by the central lab, will not be communicated to the sites so that they cannot deduce the treatment group of their patients based on LDL-C level attained. The sponsor's operational team will not have access to lipid parameters after randomization and until after the final database lock has occurred.

8.3.1.2 *Anti-alirocumab antibodies*

Patients' anti-alirocumab antibody results will not be communicated to the sites during the study.

The sponsor's operational team will not have access to anti-alirocumab antibodies associated with patient identification until after the final database lock has occurred.

The lab technicians involved in the determination of patients' anti-alirocumab antibodies are excluded from the operational team and a process will be set up to prevent any potential unblinding.

Patients who have a titer at or above 240 for anti-alirocumab antibody at follow-up visit will have additional antibody sample(s), at 6 to 12 months after the last dose and thereafter, about every 3 to 6 months until titer returns below 240.

In order to maintain the blind of the study, the requests for sample collection of post-study anti-alirocumab antibodies will also be made on patients with titers below 240 at the follow-up visit (sham request).

8.3.1.3 *Pharmacokinetics measurements*

At the assay institutions charged for PK measurements, samples will be analyzed prior to data base lock leading to unblinding of responsible bioanalysts. Bioanalysts are excluded from the operation's team and a process is set up to prevent any potential unblinding.

8.3.1.4 *Committees*

The independent CEC will review and adjudicate their respective events in a blinded manner.

The DMC will receive blinded by treatment group or unblinded (if necessary) confidential reports from an independent statistician for review ([Section 6.3](#)).

8.3.2 *Randomization code breaking during the study*

In case of an adverse event, the code must be broken by the site only in exceptional circumstances when knowledge of the IMP is essential for treating the patient. If possible, a contact should be initiated with the Monitoring Team/Medical Monitor before breaking the code. All calls will be documented by the Monitoring Team as appropriate to include date and time of the call, name of the person contacted within the Monitoring Team, patient ID, documentation of the request, and decision for unblinding or not.

Code breaking can be performed at any time by using the proper module of the centralized treatment allocation system and/or by calling any other phone number provided by the Sponsor for that purpose. However, it is preferable to contact the Medical Monitor to discuss the case before unblinding the case. If the blind is broken, the Investigator should document the date, time of day, and reason for code breaking, and report this information (or "relevant information as required by") on the appropriate page of the electronic-Case Record Form (e-CRF).

Note that when documenting the reason for unblinding, the Investigator must not provide any detail regarding the nature of the IMP. The Investigator should not divulge IMP detail to the Sponsor's representative or to any staff members until database closure. Furthermore, when completing forms (eg, AEs, SAEs), the study treatment should not be disclosed on the forms.

The code-breaking can also be performed by contacting the "24 hour alert system"; but this system should be used in very exceptional cases only (ie, unavailability of a centralized treatment allocation system or inability to contact Investigator and/or site staff). However, the preferred option is to unblind using a centralized treatment allocation system. The Investigators will be informed by the clinical monitoring team about the availability of the local code-breaking details (through an emergency centralized 24 hour telephone system for use with e-SMS). A patient card, including the relevant "24 hour alert system" telephone number will be provided to every patient who will participate in the study.

Unblinding may also be performed by the Sponsor for some SAEs that are both related and unexpected in order to conform to regulatory reporting requirements.

8.4 METHOD OF ASSIGNING PATIENTS TO TREATMENT GROUP

Two randomized lists of treatment kit numbers will be generated centrally by Sanofi. The IMP (alirocumab 75 mg, 150 mg, or placebo for alirocumab kits and ezetimibe or placebo for ezetimibe kits) will be packaged in accordance with these 2 lists.

The Trial Supply Operations Manager will provide the randomized list of treatment kit numbers and the Study Biostatistician will provide the randomization scheme to the centralized treatment allocation system provider. Then, this centralized treatment allocation system provider will generate the patient randomization list according to which it will allocate the treatment kits to the patients.

Patients will be randomized to receive either alirocumab or ezetimibe during the double-blind study treatment period using a ratio 2:1, with permuted-block randomization. Randomization will be stratified according to prior history of MI or ischemic stroke [Yes/No], statin treatment (atorvastatin 40 to 80 mg daily or rosuvastatin 20 to 40 mg daily versus simvastatin whatever the dose daily, atorvastatin below 40 mg daily or rosuvastatin below 20 mg daily) and Country/region.

The treatment kit numbers will be allocated using the centralized treatment allocation system on randomization visit (Day 1, Week 0), and then at Week 12, as re-supply visits, and at unscheduled visits, if needed.

For patients in the alirocumab treatment arm, the treatment kit allocated at week 12 will be based on their week 8 LDL-C level following the up-titration rules (see [Section 6.1](#)).

Before randomizing a patient, the Investigator or designee will have to contact the centralized treatment allocation system.

A randomized patient is defined as a patient who is registered and assigned with a treatment kit number from the centralized treatment allocation system, as documented from its log file. A patient cannot be randomized more than once in the study. If a treatment is used without contacting the centralized treatment allocation system patient will be considered as not randomized and withdrawn from the study.

Two types of centralized treatment allocation system will be used, the IVRS and the IWRS depending on the choice of the site.

8.5 DOSE UP-TITRATION

During the DBTP, patients randomized to alirocumab will receive a dose of 75 mg of the IMP from randomization (V3) up to Week 12 (V6) (ie, Weeks 0, 2, 4, 6, 8, and 10) + placebo for ezetimibe PO daily. At the Week 12 visit (V6) these patients will, in a blinded manner, either:

- Continue alirocumab 75 mg Q2W from Week 12 onwards until the last injection at Week 22 + Placebo for ezetimibe PO daily, if the Week 8 LDL-C is <70 mg/dL (1.81 mmol/L)

OR

- Dose up-titrate to alirocumab 150 mg Q2W from Week 12 onwards until the last injection at Week 22, + Placebo for ezetimibe PO daily if the Week 8 LDL-C is \geq 70 mg/dL (1.81 mmol/L).

NOTE: Lipid values obtained at Week 8 for the purpose of up-titration will not be communicated to investigators to maintain the blind. The continuation of the 75 mg dose or dose up-titration to the 150 mg dose will occur automatically through IVRS/IWRS process without site or patient awareness.

Patients randomized to ezetimibe will receive placebo for alirocumab SC Q2W until the last injection at Week 22 + ezetimibe 10 mg PO daily from randomization (V3) up to Week 24 (V8).

8.6 PACKAGING AND LABELING

Packaging is in accordance with the administration schedule.

For the DBTP, each double-blind alirocumab treatment kit, either alirocumab or placebo for alirocumab, will be supplied in kits of ready to use autoinjectors (see [Section 8.1](#)). Each kit will be prepared to contain 6 auto injectors in a mimic child-resistant package for a 12 week supply of alirocumab or placebo (ie, each autoinjector provides 2 weeks of treatment). The content of the labeling is in accordance with the local regulatory specifications and requirements.

In order to protect the blind, all alirocumab double-blind treatment kit boxes will have the same look and feel and therefore will be labeled with a double-blind label.

In addition to the alirocumab double-blind treatment kits, a training kit containing 1 placebo for alirocumab auto injector will be prepared for the purpose of instructing patients on injection administration which is to be performed prior to randomization at the injection training visit (Week -1, V2). If deemed necessary, a second injection training with placebo for alirocumab can be performed before the randomization visit using an additional training kit.

The double-blind ezetimibe kits, either ezetimibe 10 mg or placebo for ezetimibe, will be prepared to contain 3 monthly child resistance wallets of 36 capsules in each.

In order to protect the blind, all ezetimibe double-blind treatment kit boxes will have the same look and feel and therefore will be labeled with a double-blind label.

8.7 STORAGE CONDITIONS AND SHELF LIFE

Alirocumab will be shipped to the sites at 2°C to 8°C on an as-needed basis.

At sites, the alirocumab IMP kits (alirocumab or placebo for alirocumab) will be stored in a refrigerator between +2°C and +8°C (36°- 46°F) by the site. The temperature of the site refrigerator should be checked daily and recorded on a log sheet. Based on ongoing real time and accelerated stability data, as well as research stability data, alirocumab is stable until the date specified on the labels.

The ezetimibe kits (ezetimibe 10 mg or placebo for ezetimibe) will be stored between +2°C and +30°C (36°- 86°F) by the site. The temperature of the site storage room should be checked weekly at least and recorded on a log sheet.

The IMP that will be stored at the investigational site should be kept in an appropriate locked room, under the responsibility of the Investigator or designee or other authorized person in accordance with the storage conditions indicated on the label.

Physician or other authorized persons (eg, pharmacists) are responsible for storing the study product(s) in a secure and safe place in accordance with local regulations, labeling specifications, policies, and procedures.

Control of study product(s) storage conditions, especially control of temperature (eg, refrigerated storage) and information on in-use stability and instructions for handling the Sanofi compound should be managed according to the rules provided by the Sponsor.

After the supply of IMP kits to patients at the study site visits, appropriate provisions will be in place for transportation of the alirocumab IMP kits from the study site to the patient's refrigerator.

8.8 RESPONSIBILITIES

The Investigator, the hospital pharmacist, or other personnel allowed to store and dispense the IMP will be responsible for ensuring that the IMP used in the clinical trial is securely maintained as specified by the Sponsor and in accordance with applicable regulatory requirements.

All IMP will be dispensed in accordance with the Clinical Trial Protocol and it is the Investigator's responsibility to ensure that an accurate record of IMP issued and returned is maintained.

Any quality issue noticed with the receipt or use of an IMP (deficiency in condition, appearance, pertaining documentation, labeling, expiration date, etc) should be promptly notified to the Sponsor. Some deficiencies may be recorded through a complaint procedure.

A potential defect in the quality of IMP may be subject to initiation of a recall procedure by the Sponsor. In this case, the Investigator will be responsible for promptly addressing any request made by the Sponsor, in order to recall IMP and eliminate potential hazards.

Under no circumstances will the Investigator supply IMP to a third party, allow the IMP to be used other than as directed by this clinical trial protocol, or dispose of IMP in any other manner.

8.8.1 Treatment accountability and compliance

IMP administration data will be recorded by the patients onto a patient's diary.

Measures taken to ensure and document IMP compliance and accountability are described below:

- The Investigator or designee will obtain via IVRS/IWRS the treatment kit numbers and he/she will dispense the treatment kits to the patient.
- The accountability is to be performed at alirocumab IMP kit re-supply visits only (see [Section 10.1.2](#)). The used and unused IMP kit(s) should be brought back to such visits for accountability purposes. Sharps container will be supplied to each patient for used auto injectors. The patients should return it to the site for destruction purpose at the end of study participation.
- All ezetimibe kits are returned by the patient at the designated visit.
- The Investigator or designee will complete the corresponding treatment log form from patient's diary.
- The Investigator/study coordinator will enter data in the appropriate e-CRF pages, according to data recorded in the treatment log form.
- The monitor will check the data consistency between e-CRF pages, treatment log forms using patient's diary, and returned unused auto-injectors or capsules of a corresponding kit.

8.8.2 Return and/or destruction of treatments

It is Sanofi's responsibility to ensure the destruction of all used or unused alirocumab. All used and unused treatments kits will be retrieved by the Sponsor or destroyed on site, depending on local requirements.

A detailed treatment log of the returned and destroyed IMP will be established with the Investigator or designee and countersigned by the Investigator and the Monitoring Team.

The physician will not destroy the used or unused autoinjectors unless Sanofi provides written authorization.

8.9 CONCOMITANT MEDICATION

A concomitant medication is any treatment received by the patient concomitantly to the study (from screening visit until follow-up visit).

Concomitant medications should be kept to a minimum during the study. However, if these are considered necessary for the patient's welfare and are unlikely to interfere with the IMP, they may be given at the discretion of the Investigator, with a stable dose (when possible). Besides the specific information related to concomitant medications provided in this section, any other concomitant medication(s) will be allowed and will have to be recorded in the e-CRF and source data.

For background statins (and any additional LMT as per [Section 8.9.1](#)), sites must follow the national product label for the safety monitoring and management of patients.

Nutraceutical products or over-the-counter therapies that may affect lipids are allowed only if they have been used at a stable dose for at least 4 weeks prior to screening visit, during the screening period and maintained during the 24 weeks of the DBPT. Examples of such nutraceutical products or over-the-counter therapies include omega-3 fatty acids at doses <1000 mg, plant stanols such as found in Benecol, flax seed oil, and psyllium.

8.9.1 Management of background lipid modifying therapy / Rescue therapy

Patients must have been on stable maximally tolerated daily registered doses of statins for at least 4 weeks before screening visit.

During the study, the patients should stay on these stable maximally tolerated registered daily doses of statins. Lipid profile values from samples obtained after randomization will be blinded. Nevertheless, sites will be made aware of TG alert, in order to make decisions on the patient's background LMT.

From the screening visit (Week -3) until Week 24 of the DBPT, the background LMT should not be changed. No dose adjustment, discontinuation or initiation of other statins should take place during this time, barring exceptional circumstances whereby overriding concerns (including but not limited to TG alert posted by the central lab) warrant such changes, as per the investigator's judgment.

For a TG alert (see [Section 10.6.4](#)) that has been confirmed by repeat testing, the investigator should perform investigations, manage the patient, and modify the background LMT as per his/her medical judgment.

In summary, background statin therapy should not be modified from screening to the follow up visit. However, up to Week 24, if a confirmed TG alert is reached or if there is an overwhelming clinical concern (at the discretion of the investigator) then modification of the background LMT is allowed.

8.9.2 Contraception

Women of childbearing potential must take an effective contraceptive method throughout the study treatment and for 10 weeks after the last intake of IMP (injection or capsule, whichever comes last) (eg, Follow-up visit).

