7.2.3 Exclusion criteria related to the current knowledge of alirocumab

- E 35. Known hypersensitivity to monoclonal antibody or any component of the drug products
- E 36. Pregnant or breast-feeding women
- E 37. Women of childbearing potential not protected by highly-effective method(s) of birth control and/or who are unwilling or unable to be tested for pregnancy

NOTE: Women of childbearing potential must have a confirmed negative pregnancy test at screening and randomization visits. They must use an effective contraceptive method throughout the entire duration of the study treatment, and for 10 weeks after the last intake of IMP (injection or capsule, whichever come last), and agree to repeat urine pregnancy test at designated visits. The applied methods of contraception have to meet the criteria for a highly effective method of

birth control according to the ‘Guidance on nonclinical safety studies for the conduct of human clinical trials and marketing authorization for pharmaceuticals’ (45). Postmenopausal women must be amenorrheic for at least 12 months.

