8.1.2 Timing of administration

A training injection is planned on Week -1 (V2) with a placebo for alirocumab. A second training injection with placebo for alirocumab may be administered between Week -1 and randomization visit.

During the double-blind treatment period, alirocumab or placebo for alirocumab will be administered SC Q2W, starting at Week 0 continuing up to the last injection (Week 22) 2 weeks before the end of the DBTP. If the injection is scheduled to take place on the same date as the site visit, then the IMP should be administered after the blood sampling has been completed.

Further training with the scheduled double-blind alirocumab IMP can be done between W 0 and W 4 and at additional scheduled or unscheduled visits, as per investigator's judgment.

Double-blind IMP will start as soon as possible after the call for randomization using the treatment kit number provided by the IVRS/IWRS. The first injection after randomization will be done at the site by the patient or another designated person (such as spouse, relative, etc) under direct site staff supervision. Patients will be monitored at the investigational site for at least 30 minutes after this first double-blind injection.

Alirocumab IMP injection should be administered Q2W SC at approximately the same time of the day; however it is acceptable to have a window period of ± 3 days. The time of the day is based on patient's preference.

If by mistake or due to other circumstances an injection is delayed by more than 7 days or completely missed, then the patient should return to the original schedule of study treatment administration without administering delayed injections. On the other hand, if the delay is less than or equal to 7 days from the missed date, then the patient should administer the delayed injection and then resume the original schedule of study treatment administration.

Ezetimibe 10 mg or placebo for ezetimibe capsules will be taken orally once daily at approximately the same time of the day, with or without food. Preferably, on the injection days the IMP capsule will be administered roughly at the time of injection (either before or shortly after). The capsules must be taken until the day before the end-of-treatment visit (early or not), and not stopped at the time of the last injection.

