10.1.2.5 Visit 8/Week 24 (Day 169 ± 3): End of treatment visit

- Collect AEs
- Record concomitant medication
- Get body weight measurement
- Take vital signs including HR and BP
- Review patient's diet. Patient should be on a NECP-ATP III TLC diet or equivalent
- Perform 12-lead ECG
- Perform physical examination
- IVRS/IWRS contact to document the end of treatment
- Data collection on IMP administration and IMP compliance check by review of diary and treatment kit accountability.
- Urinalysis
- Urine pregnancy test (WOCBP only).

- Obtain fasting blood sample for:
 - Anti-alirocumab antibodies (to be performed prior to the IMP injection).
 - Lipids: measure and/or calculation of TC, LDL-C, HDL-C, TG, non-HDL-C, Apo B, Apo A-1, Apo B/Apo A-1 ratio and Lp(a)
 - Library samples
 - Hematology: CBC including RDW and reticulocyte count, hematocrit, Hb, red blood cell count, white blood cell count with differential blood count and platelet
 - Chemistry: glucose, sodium, potassium, chloride, bicarbonate, calcium, phosphorous, urea nitrogen, creatinine, uric acid, LDH, total protein, albumin and γ GT
 - Hepatitis C Antibody Test (with automatic confirmatory testing if positive)
 - HbA1c
 - Liver panel (ALT, AST, ALP, and total bilirubin)
 - CPK
 - Serum alirocumab concentration (PK)
- Reminders
 - An appointment will be given for the next study site visit.
 - Remind patient to be in fasting conditions (ie, overnight, at least 10-12 hours fast and refrain from smoking) for next study site visit, if needed. Also, alcohol consumption within 48 hours and intense physical exercise within 24 hours preceding the next study site visit are discouraged.
 - Sharp-container (containing all used auto-injectors) must be returned at site for destruction.

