10.1.3 Follow-Up Period

10.1.3.1 Follow-Up Visit (Visit 9/ Week 32/ Day 225 \pm 7)

- Collect AEs
- Record concomitant medication
- Get body weight measurement
- Take vital signs including HR and BP.
- Perform physical examination (only in case of clinically relevant abnormality at the end of treatment visit)
- IVRS/IWRS contact to document the end of study
- Urinalysis (only in case of clinically relevant abnormal value at the end of treatment visit)
- Urine pregnancy test (WOCBP only)
- Obtain fasting blood sample for:

- Anti-alirocumab antibodies (as per schedule note in study flowchart of [Section 1.2](#))
- Only in case of clinically relevant abnormal values for these parameters at the end of treatment visit will the following be obtained at this visit:
 - a) Hematology: CBC including RDW and reticulocyte count, hematocrit, Hb, red blood cell count, white blood cell count with differential blood count and platelet
 - b) Chemistry: glucose, sodium, potassium, chloride, bicarbonate, calcium, phosphorous, urea nitrogen, creatinine, uric acid, LDH, total protein, albumin and γ GT
 - c) HbA1c
 - d) Liver panel (ALT, AST, ALP, and total bilirubin)
 - e) CPK

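### For a woman who completes treatment, the visit named as an example of when contraception may end falls 13 days before the protocol's own 10-week period is over

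*Protocol*

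**What the plan says.** The contraception rule appears twice in the protocol. Section 8.9.2 sets it "for 10 weeks after the last intake of IMP (injection or capsule, whichever comes last) (eg, Follow-up visit"). The note to exclusion criterion E 37 in Section 7.2.3 repeats the duration and the starting event, "for 10 weeks after the last intake of IMP (injection or capsule, whichever come last), and agree to repeat urine pregnancy test at designated visits", but names no visit as the end.

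The two products stop at different times. Section 8.1.2 has injections "continuing up to the last injection (Week 22) 2 weeks before the end of the DBTP". Of the oral product it says: "The capsules must be taken until the day before the end-of-treatment visit (early or not), and not stopped at the time of the last injection".

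The visits that matter are "Visit 8/Week 24 (Day 169 ± 3): End of treatment visit" (Section 10.1.2.5) and the follow-up visit, "Visit 9/ Week 32/ Day 225", with a window of 7 days either side (Section 10.1.3.1). The flow chart (Section 1.2) schedules urine pregnancy tests at Weeks 0, 12, 24 and 32, and none later. Section 10.4.3 ends routine adverse event recording at the follow-up visit.

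**The concern.** The rule counts from whichever product is taken last. For a woman who completes treatment that is the capsule. The visit offered as an example of the end point fits a count from the last injection instead. One sentence therefore points to two dates, and two sites could each cite it when giving a patient different stop dates.

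This is an operative instruction that sites and patients follow literally. A site that works from the named visit would end contraception before the period the protocol itself sets. For that patient, the remaining days of the stated period would also have no scheduled pregnancy test, no visit and no routine adverse event collection.

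**Working it through.** **Inputs**
- Day numbering: day = 7 × week + 1, which matches the flow chart (Week 24 = Day 169, Week 32 = Day 225).
- Last injection, Week 22 (8.1.2): 7 × 22 + 1 = Day 155.
- Last capsule, the day before the Week 24 visit (8.1.2): 169 − 1 = Day 168.
- Required duration (7.2.3 and 8.9.2): 10 × 7 = 70 days.
- Follow-up visit (10.1.3.1): Day 225.

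**The protocol's own figure.** Section 4 describes the 8-week follow-up as reaching 10 weeks after last dosing. Counted from the last injection this reproduces: 155 + 70 = 225, and 169 + 56 = 225.

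**The contraception rule as worded.** Counted from the later intake, the capsule: 168 + 70 = Day 238. The gap to the named visit is 238 − 225 = 13 days. At that visit the patient is 225 − 168 = 57 days, or 57 / 7 = 8.1 weeks, past her last capsule.

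**Is the capsule always the later intake for a completer?** Section 8.1.2 allows a delayed injection to be given up to 7 days late, so at the latest on 155 + 7 = Day 162. The earliest Week 24 visit is Day 166, which puts the last capsule on Day 165. The capsule is still later.

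**Visit windows.** Section 10 says that when one visit moves, the next stays on the original schedule. The two windows therefore vary independently.
- Week 24, Day 169 ± 3: last capsule on Days 165 to 171, so 10 weeks end on Days 235 to 241.
- Week 32, Day 225 ± 7: Days 218 to 232.
- Smallest gap: 235 − 232 = 3 days. Largest gap: 241 − 218 = 23 days.

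If follow-up were instead timed 56 ± 7 days from the actual Week 24 visit, the gap would be 70 − 1 − 56 = 13, plus or minus 7, or 6 to 20 days. Section 10 does not schedule it that way. Under neither reading does the gap close.

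**Who is not affected.** On the nominal calendar, Day 225 is at least 10 weeks after last intake for anyone whose last injection and last capsule both fall on or before 225 − 70 = Day 155. That covers many who stop early but keep to the visit schedule. Section 10.3.4 also lets those who stop treatment and decline to continue have a final visit 10 weeks after stopping.

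**The case against.** The best reply is that the protocol has one rule and one poor example. The duration is stated twice as an obligation, while the visit appears once, in brackets, introduced as an example, and E 37 does not mention it. A site would have to follow the example and ignore the duration in the same sentence. This stands to the extent that the protocol cannot be said to equate the visit with the end of contraception. It does not remove the conflict, because the example is wrong for the ordinary completer.

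A reader might infer three stronger points that the documents do not support.

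- **The last pregnancy test contradicts the rule.** E 37 asks for tests at designated visits. Nothing requires the last test to fall at or after the end of contraception, so its timing is a consequence to consider and not a second contradiction.
- **Patients are exposed to a documented risk.** The 10-week period is explained by residual alirocumab: Section 4 counts from last dosing, and Protocol 9.2 and SAP 2.1.4 count 70 days from the last injection. No 10-week residual effect is described for the capsule, and the only capsule-based offset, in the efficacy treatment period (11.3.1.2), is 3 days. This does not settle which clock should apply, but it means that the finding is a mismatch with a stated rule, not a demonstrated hazard.
- **Pregnancies would go unrecorded.** Section 10.4.5.1 makes pregnancy an event of special interest with immediate notification and follow-up to outcome, so capture does not rest on the scheduled urine test alone. What remains is that routine collection ends at the follow-up visit.

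**Conclusion.** The point holds as an internal inconsistency. For a woman of childbearing potential who takes both products to the end of the planned period, the visit in the example comes 13 days before the stated duration ends on the nominal schedule, and 3 to 23 days before across the Week 24 and Week 32 windows. This assumes that capsules are taken as Section 8.1.2 directs and that visits keep to the original calendar as Section 10 directs.

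It does not extend to every woman in the trial, since early discontinuers may have passed 10 weeks by their last visit. The documents give no number of women of childbearing potential, so the number affected cannot be stated. The matter is minor: no endpoint, analysis population, sample size or error rate depends on it.

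**What to change.** Reconcile Protocol 8.9.2 and the E 37 note in 7.2.3 with the capsule instruction in 8.1.2, the flow chart in 1.2 and the follow-up visit in 10.1.3.1, so that the starting event, the duration and any named visit lead to the same date. Then check the last pregnancy test and the end of routine adverse event collection against that date. Which clock applies is a decision for the sponsor's clinical team, and this review takes no position on it.

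The cost is a few words in the protocol. If the reconciled period ends after the follow-up visit, the timing of the last test also has to be considered. The consent form was not available, so whether it carries the same wording should be checked. The statistical analysis plan needs no change.
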